8.8 Safety analyses

8.8.1 Evaluations

Safety and tolerability will be evaluated by solicited local and systemic reactions (immediate complaints within 15 minutes post-vaccination and solicited reactions up to seven days post-vaccination), unsolicited AEs up to 21 days post-vaccination, and SAEs and NOCDs up to the end of the surveillance period.

Subjects will be monitored for both solicited local reactions (erythema, swelling, and pain at the injection site) and solicited systemic reactions (fever, headache, fatigue, muscle aches, joint aches, chills, a feeling of general discomfort, swelling in the axilla, and swelling in the neck) from the time of vaccination through Day 7. While the subjects remain in the clinic following vaccine administration, staff will monitor them for immediate local and systemic reactions; after release from the clinic facility, from the evening of Day 0 to the evening of Day 7, subjects will measure and record their local and systemic reactions in their eDiary.

The intensity of the solicited local and systemic reactions will be graded as: mild (1), moderate (2), severe (3) or potentially life threatening (4). Their causal relationship with the study vaccine will be assessed by the Investigator (definitely not related, probably not related, possibly related, probably related or definitely related).

[Table 4](#) shows severity grades for solicited local and systemic reactions.

Table 4 Severity Grades for Solicited Local and Systemic Reactions

Symptoms	Severity				
	None	Grade 1 (Mild)	Grade 2 (Moderate)	Grade 3 (Severe)	Grade 4 (Potentially life-threatening)
Injection Site Reactions (Local Reactions)					
Erythema (redness)	< 25 mm	25 - 50 mm	51 - 100 mm	> 100 mm	Necrosis or exfoliative dermatitis
Swelling	< 25 mm	25 - 50 mm and does not interfere with activity	51 - 100 mm or interferes with activity	> 100 mm or prevents daily activity	Necrosis
Pain	None	Does not interfere with activity	Repeated use of non-narcotic pain reliever for more than 24 hours or interferes with activity	Any use of narcotic pain reliever or prevents daily activity	Results in a visit to emergency room (ER) or hospitalization
Solicited Systemic Reactions					
Fever (°C or °F)	< 38.0 °C < 100.4 °F	38.0 - 38.4 °C 100.4 - 101.1 °F	38.5 - 38.9 °C 101.2 - 102.0 °F	39.0 - 40.0 °C 102.1 - 104.0 °F	> 40.0 °C > 104.0 °F
Headache	None	No interference with activity	Repeated use of non-narcotic pain reliever for more than 24 hours or some interference with activity	Significant; any use of narcotic pain reliever or prevents daily activity	Results in a visit to emergency room (ER) or hospitalization
Fatigue	None	No interference with activity	Some interference with activity	Significant; prevents daily activity	Results in a visit to emergency room (ER) or hospitalization
Muscle aches	None	No interference with activity	Some interference with activity	Significant; prevents daily activity	Results in a visit to emergency room (ER) or hospitalization
Joint aches, chills, feeling of general discomfort or uneasiness (malaise), swelling in the axilla, swelling in the neck	None	No interference with activity	Some interference with activity not requiring medical intervention	Prevents daily activity and requires medical intervention	Results in a visit to emergency room (ER) or hospitalization

8.8.2 Adverse events

All Adverse events (AEs) will be classified by Primary SOC and PT according to the Medical Dictionary for Regulatory Activities® (MedDRA®) Version 19.0 or higher.

All AEs occurring within 21 days after vaccination will be reported in the “Adverse Event” screen in the subject’s eCRF, irrespective of intensity or whether or not they are considered to be vaccination-related. Thereafter, from Day 22 to the end of the surveillance period, SAEs, AEs leading to withdrawal, and NOCDs will be monitored and reported in the eCRF.

The intensity of AEs will be graded as: mild (1), moderate (2), severe (3) or potentially life threatening (4), according to the Food and Drug Administration (FDA) Guidance for Industry (FDA, 2007). Their causal relationship with the study vaccine will be assessed by the Investigator (definitely not related, probably not related, possibly related, probably related or definitely related); see Section 13.1.9 in protocol for a definition of these causal relationships.

8.8.3 Secondary Endpoints

The secondary endpoints of safety that are mentioned in section 4.2.1 will be analysed as follows:
All safety analyses will be based on the SAS.

Safety and tolerability endpoints (immediate complaints, solicited local and systemic reactions, and TEAEs, deaths, SAEs, AEs leading to subject withdrawal, and NOCDs) will be summarized by treatment group and by age group using descriptive statistics.

The original terms used in the eCRFs by Investigators to identify AEs will be coded using the MedDRA®. All eCRF reported AEs with onset post-vaccination will be included in the safety analyses.

Special attention will be given to those subjects who die, who discontinue from the study due to an AE, who experience an SAE (e.g. summaries, listings, and narrative preparation will be provided, as appropriate), or who experience an allergic or allergic-like reaction (hypersensitivity cases).

Overall summaries of subjects with solicited reactions and Unsolicited Treatment Emergent Adverse Events (TEAE) will be prepared as follows:

- Subjects with any solicited reactions or unsolicited TEAEs
- Any solicited local and systemic reactions occurring 15 minutes after vaccination (immediate complaints)
- Solicited reactions including immediate complaints
- Severe and potentially life-threatening solicited reactions
- Severe and potentially life-threatening related solicited reactions
- Solicited local reactions
- Solicited systemic reactions
- Unsolicited TEAEs (Day 0 to Day 21)
- Related unsolicited TEAEs

- Severe and potentially life-threatening unsolicited TEAEs
- Severe and potentially life-threatening related unsolicited TEAEs
- Serious TEAEs (Day 0 to Day 21)
- Serious TEAEs (Day 0 to End of study)

The percentage of subjects with at least one immediate complaint (local or systemic reactions) and the percent of subjects with at least one immediate complaint of each of the individual local and systemic reactions will be summarized by treatment group and by age group.

In addition, the same summary will be tabulated by maximum severity grading and by causality for each treatment group overall and by age group.

The maximum event severity will be considered to be the greatest severity associated with each reaction according to the following order: mild < moderate < severe < potentially life-threatening. Causality will be presented as “Unrelated” (definitely not related and probably not related) and “Related” (possibly related, probably related and definitely related).

Similar summaries will be presented for solicited local and systemic reactions collected from Day 0 to Day 7 and unsolicited TEAEs collected up to Day 21. In addition, summaries of severe and potentially life-threatening solicited local and systemic reactions and unsolicited TEAEs will also be provided.

The analysis of unsolicited adverse events comprises the following categories:

- Occurrence of any unsolicited TEAE by system organ class (SOC) and PT from the administration of the vaccine dose up to day 21 (day 0 to day 21)
- Unsolicited TEAEs by SOC, PT and Maximum severity (Day 0 to 21)
- Unsolicited TEAEs by SOC, PT and relationship status (Day 0 to 21)
- Grade 3 and Grade 4 related unsolicited TEAEs by SOC and PT (Day 0 to Day 21)

AE summary tables will be presented for the below categories as well:

- AEs leading to death (Day 0 to End of study)
- Serious TEAEs (Day 0 to Day 21) by SOC and PT
- Serious TEAEs (Day 0 to End of study) by SOC and PT
- AEs leading to withdrawal (Day 0 to End of study)
- Occurrence of New Onset of a Chronic Disease (NOCD)s (Day 0 to Day 21) by SOC and PT
- Occurrence of NOCDs (Day 0 to End of study) by SOC and PT

- Occurrence of Hypersensitivity Cases (Day 0 to Day 21) by SOC and PT

Events that are considered to be a new onset of chronic disease (NOCD), as defined in the study protocol, will be collected until the end of surveillance. A summary of the occurrence of NOCDs, by SOC and PT, will be provided for Day 0 to Day 21 and from Day 0 to the end of surveillance.

Hypersensitivity cases will be identified using a standardized MedDRA® query (SMQ) for hypersensitivity. A summary of the occurrence of hypersensitivity events, by SOC and PT, will be provided for Day 0 to Day 21 and from Day 0 to the end of surveillance.

In summaries by SOC and PT, events will be sorted by internationally order (please refer [Appendix A](#)).

Where the same reaction or same adverse event, based on preferred terminology, is reported multiple times for the same subject in a treatment period, the subject will only be counted once in the preferred terminology level in summary frequency tables.

Individual listings will be provided for the categories below:

- Solicited local and systemic reactions Day 0 to Day 7
- Unsolicited AEs (Day 0 to Day 21)
- Serious TEAEs (Day 0 to end of surveillance)
- NOCD (Day 0 to End of Study)
- Hypersensitivity Cases (Day 0 to End of study)

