### **13.1.3 Adverse Events of Special Interest**

Based on the data from the five studies conducted to date, there is no evidence of anaphylactic reactions associated with use of the Quadrivalent VLP Influenza Vaccine in humans: a small number of subjects had potential hypersensitivity reactions judged to be related to vaccine administration (no more than 0.3 % of subjects in any given VLP treatment group experienced one of these events) and the events were distributed fairly evenly among treatment groups,

---

Confidential Information

including the placebo and the active comparator groups. However, since severe reactions are considered to be an important potential risk (based on the theoretical risk that using plants for the production of biotherapeutics may induce hypersensitivity) the sponsor will continue to require that appropriate medical treatment and supervision are available to manage any possible anaphylactic reactions.

To collect additional data on these events, Medicago will closely monitor and assess allergic or allergic-like reactions as AEs of special interest. Thus, to collect specific data under this protocol, the Investigator should, whenever possible, take a picture of any occurrence of allergic or allergic-like reactions and send the anonymized images to Medicago as described in the Study Procedure Manual.

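### The SAP's hypersensitivity summary and listing from Day 0 to the end of follow-up omit some non-serious allergic reactions after Day 21, and nothing labels them as restricted

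*SAP*

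**What the plan says.** **What is to be reported.** SAP 8.8.3 finds cases by a standardized MedDRA "query (SMQ) for hypersensitivity". It states that a summary of "hypersensitivity events, by SOC and PT, will be provided for Day 0 to Day 21 and from Day 0 to the end of surveillance". The individual listings at the end of the section include one of hypersensitivity cases from Day 0 to the end of the study. The bulleted list of AE tables earlier in the same section has a single hypersensitivity entry: "Occurrence of Hypersensitivity Cases (Day 0 to Day 21) by SOC and PT".

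**What is to be collected.** SAP 8.8.2 has two rules. To Day 21: "All AEs occurring within 21 days after vaccination will be reported", whatever their intensity or causality. After that: "from Day 22 to the end of the surveillance period, SAEs, AEs leading to withdrawal, and NOCDs will be monitored and reported". Protocol 10.3.1.2, 13.1.2 and Table 1 note 7 say the same.

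**Why these events are singled out.** Protocol 13.1.3 treats severe reactions as an important potential risk, because of the theoretical risk of hypersensitivity to a plant-made product, and says that "Medicago will closely monitor and assess allergic or allergic-like reactions as AEs of special interest". It gives these events no collection window, and they are not among the categories recorded from Day 22. Protocol 1.3.2.2 drops the plant-glycan assessment and relies on continued monitoring of allergic-like reactions.

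**The concern.** The longer summary joins two collection rules: every AE up to Day 21, then three categories only. Nothing in the SAP says that the table or the listing is restricted in its second part. A reader would take the percentage as the rate of the product's named risk over the whole of follow-up. A subject with an acute, self-limited allergic reaction after Day 21 that is not serious, not a new chronic disease and not a cause of withdrawal would be counted as event-free. A low rate in that table could then be quoted as reassurance that the data cannot give.

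The section also disagrees with itself on which tables to produce. The table list asks for one hypersensitivity window, and the text a few lines later asks for two.

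**Working it through.** The plan gives no figure to reproduce here. The check compares the windows and then counts days.

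**Step 1. Reporting window against collection window.**

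| Output in SAP 8.8.3 | Window reported | Events collected throughout that window? |
|---|---|---|
| Serious TEAEs | Day 0-21 and Day 0-end | Yes, both |
| NOCDs | Day 0-21 and Day 0-end | Yes, both |
| Hypersensitivity, table list | Day 0-21 | Yes |
| Hypersensitivity, text | Day 0-21 and Day 0-end | First yes; second only in part |
| Hypersensitivity, listing | Day 0-end | Only in part |

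Serious TEAEs and NOCDs are collected to the end, so their longer tables are complete. A MedDRA query can return only AEs that were recorded, so the longer hypersensitivity output cannot be complete.

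**Step 2. How much of the window has full collection.** Day 0 to Day 21 inclusive is 22 days. Let T be the number of days from Day 0 to 30 April 2018 inclusive. The protocol Synopsis puts vaccination in August to September 2017 in North America and Europe, and at about the beginning of November in Asia. The exact dates below are assumptions within those ranges, and the end date is itself approximate.

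| Day 0 assumed | T (days) | 22/T | Restricted, (T − 22)/T |
|---|---|---|---|
| 1 August 2017 | 273 | 8.1% | 91.9% |
| 30 September 2017 | 213 | 10.3% | 89.7% |
| 1 November 2017 | 181 | 12.2% | 87.8% |

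These are shares of calendar time.

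**Step 3. What share of events the longer table could hold.** Let e be the share of all hypersensitivity events that fall in Day 0-21, and s the share of later events that are SAEs, NOCDs or causes of withdrawal. Then

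share captured = e + s(1 − e).

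The documents give neither e nor s, so both are assumptions.

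- Constant rate over follow-up, e = 22/T: captured 8 to 12% if s = 0; 17 to 21% if s = 10%; 26 to 30% if s = 20%. For example, with T = 273 and s = 10%: (22 + 0.1 × 251)/273 = 47.1/273 = 17.3%.
- Half of events early, e = 0.5: 50% if s = 0; 60% if s = 20%.
- Most events early, e = 0.9: 90% if s = 0; 91% if s = 10%.
- All events early, e = 1: 100% whatever s is.

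The range runs from 8% to 100%. The direction is fixed, since the table can miss events but not add them. The size is not.

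**The case against.** The best defence has five parts.

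- **Non-serious events are not all lost after Day 21.** AEs leading to withdrawal are kept. So are NOCDs, and protocol 13.1.4 defines these broadly and names an allergic component. This stands. A reader might infer that no non-serious AE is collected after Day 21, and the documents contradict that.
- **Some late reactions would count as serious.** The SAE definition in protocol 13.1.1 includes medically important events and gives allergic bronchospasm treated in an emergency room as an example. This stands for the more severe reactions. It does not reach a mild, self-limited one.
- **Other channels exist.** Subjects are asked to report changes in health (Synopsis, Safety Evaluations), the final call asks about them (10.1.6), and the memory aid notes medically attended problems from Day 22 (19.3). This stands only in part: none of these makes a non-serious event after Day 21 reportable in the eCRF as an AE.
- **A complete table already exists.** The Day 0 to 21 summary matches full collection and will be shown beside the longer one. This stands, and it limits the harm. It does not tell the reader that the longer table is restricted.
- **Stopping general AE collection at Day 21 after one injection is a deliberate choice, stated the same way throughout.** This also stands. The fault is in the reporting window, not necessarily in the collection rule.

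Two further inferences should be resisted. One is bias between arms: the same collection rule applies to both arms under observer-blinding (protocol 6.2), and the safety analysis is descriptive. The other is to size the loss from the 0.3% in protocol 13.1.3. That figure is a ceiling for vaccine-related potential hypersensitivity in any earlier VLP group, and says nothing about events after Day 21.

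**Conclusion.** The point holds in a limited form. As written, SAP 8.8.3 produces a full-period hypersensitivity summary and listing from data that after Day 21 contain only SAEs, NOCDs and AEs leading to withdrawal. If any other allergic reaction occurs after Day 21, the absolute rate of the protocol's adverse event of special interest is understated, and the output carries no warning. The table list in the same section also conflicts with the text and the listing.

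The size cannot be stated. It is tempting to read the 88 to 92% of follow-up under restricted collection as the share of events missed. That would require a constant event rate and no late event in a collected category, and the documents support neither assumption. If every event falls by Day 21, nothing is lost.

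The point is worth correcting because this is the risk that the sponsor itself singles out, and because the correction is small.

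**What to change.** **Needed, SAP 8.8.3 only.** Choose one:

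1. Delete the hypersensitivity summary from Day 0 to the end of surveillance, and end the listing at Day 21 or label it as in option 2.
2. Keep both, and title them: all events to Day 21; SAEs, NOCDs or AEs leading to withdrawal only thereafter.

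In either case, make the bulleted table list, the text and the listing name the same windows. The cost is SAP wording and table titles, with no change to data collection.

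**Optional, if a true full-period rate is wanted.** Add allergic or allergic-like reactions, as described in protocol 13.1.3, to the categories recorded from Day 22 in protocol Table 1 note 7, 10.3.1.2 and 13.1.2 and in SAP 8.8.2. The surveillance contacts, at least three a week under protocol 10.1.4, could carry the question. The cost is a protocol amendment with ethics committee approval (17.1) and an eCRF change. Any subjects already past Day 21 when it took effect would have incomplete collection for the interval before it, so the restricted label would still be needed for them.

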8.8.4 Analysis of Exploratory Endpoints

The exploratory safety endpoints defined in 4.2.2 will be analysed as follows:

The occurrences of non-routine medical visits, emergency room visits, hospitalizations, pneumonia (clinical diagnosis), new onset or exacerbations of pre-existing cardio-respiratory conditions, and number of workdays missed will be summarized by treatment using descriptive statistics and percentages (surveillance period). These analysis will be done separately and not be included in the CSR.

8.8.5 Clinical laboratory evaluations

As part of screening procedures, a urine sample will be collected for female subjects of childbearing potential for a urine dipstick pregnancy test that will be performed during the eligibility assessment on Day 0.

An individual listing will be provided for the Urine Pregnancy Test Results.

8.8.6 Vital signs

Vital signs measurements (resting BP, HR, and OT) will be performed as part of screening procedures (during eligibility assessment on Day 0) and after the 15-minute post-vaccination

surveillance period.

An individual listing will be provided for vital signs measurements by subject and age stratum.

8.8.7 Physical examinations

A history- or symptom-directed physical examination will be performed by the Investigator as part of screening procedures (during the eligibility assessment on Day 0).

An individual listing will be provided for Physical Examination results by subject and age stratum.

8.8.8 Electrocardiograms

Electrocardiograms are not planned for this study.

8.8.9 Other safety assessments

No other safety assessments are planned for this study.

8.9 Other analysis

Not planned.

8.9.1 Subgroup analysis

The following subgroup analysis will be performed for the primary efficacy endpoint.

- Age group
- Laboratory-confirmed matched influenza strain
- Sex
- Race
- Ethnicity

8.10 Intermediate analysis

The purpose and analyses performed for intermediate analysis will be included in a separate charter.

9 CHANGES TO PLANNED ANALYSIS FROM STUDY PROTOCOL

There are no changes in the analysis methods other than planned in protocol.

11 APPENDICES

Appendix A – Order of SOC (Medical History, Unsolicited Treatment-Emergent AE)

SOC *Infections and infestations*
SOC *Neoplasms benign, malignant and unspecified (incl cysts and polyps)*
SOC *Blood and lymphatic system disorders*
SOC *Immune system disorders*
SOC *Endocrine disorders*
SOC *Metabolism and nutrition disorders*
SOC *Psychiatric disorders*
SOC *Nervous system disorders*
SOC *Eye disorders*
SOC *Ear and labyrinth disorders*
SOC *Cardiac disorders*
SOC *Vascular disorders*
SOC *Respiratory, thoracic and mediastinal disorders*
SOC *Gastrointestinal disorders*
SOC *Hepatobiliary disorders*
SOC *Skin and subcutaneous tissue disorders*
SOC *Musculoskeletal and connective tissue disorders*
SOC *Renal and urinary disorders*
SOC *Pregnancy, puerperium and perinatal conditions*
SOC *Reproductive system and breast disorders*
SOC *Congenital, familial and genetic disorders*
SOC *General disorders and administration site conditions*
SOC *Investigations*
SOC *Injury, poisoning and procedural complications*
SOC *Surgical and medical procedures*
SOC *Social circumstances*
SOC *Product issues*

Table 3-2. The MedDRA Terminology SOC List – Internationally Agreed Order
